Protocol Title:

Comparison of Timing of Initiation on the Efficacy of Gabapentin in Treating
Neuropathic Pain in Spinal Cord Injury (SCI).

2/4/20

ClinicalTrials.gov Identifier: NCT04256603

Introduction:

Neuropathic pain is a common complaint in those with spinal cord injury (SCI) that has a significant negative effect on quality of life. This makes the treatment of neuropathic pain a priority in the SCI population. Efficacy of various treatments, however, remains controversial. There is evidence to support that gabapentin and pregabalin have some benefit in reducing neuropathic pain (1). Other positive effects of gabapentin on those with SCI have also been demonstrated. However, there has not been a study on the influence of timing of initiation of gabapentin on the efficacy of using it to treat neuropathic pain in the SCI population. Such a finding could change the standard of care in treatment of acute SCI.

The pooled prevalence of neuropathic pain post spinal cord injury is 53% (2). Not only common, neuropathic pain is pervasive, affecting aspects of patients' lives including sleep, physical function, and mood that in turn impact their activities—work and recreational alike (3). Thus, neuropathic pain management contributes to quality of life for a majority of people with SCI.

Although a high priority, the treatment of neuropathic pain in SCI remains notoriously difficult (4). Treatment options may be divided into pharmacologic and non-pharmacologic. Pharmacologic agents studied include amitriptyline, gabapentin, pregabalin, opiates, lidocaine, ketamine, valproate, lamotrigine, levetiracetam and carbamazepine; the most studied of which are amitriptyline, gabapentin, and pregabalin (5).

Gabapentin's potential is not limited to neuropathic pain management, making it a particularly compelling treatment option in the population with acute SCI. Gabapentin leads to improvement in total motor scores (6-9), reduced spasticity, reduced autonomic dysreflexia, and improved mood (8, 9). Animal models suggest it may be neuroprotective in the acute phase of injury (10). In those who undergo spine surgery, regardless of presence of SCI, gabapentin given perioperatively leads to reduced opiate use and decreased pain in post-operative period (11). Additionally, when compared to narcotic alternatives, gabapentin has minimal side effects.

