Neuropathic pain in SCI is common, impactful, and difficult to treat. Gabapentin is effective in the management of symptoms and concerns related to SCI including motor recovery, spasticity, and mood among others. This makes gabapentin an important pharmacologic intervention, which compels providers to define treatment guidelines related to its use. One aspect of which should relate to the timing of initiation of therapy. The goal of this study is to determine whether early initiation of treatment with gabapentin will decrease average pain scores and opiate use when compared to late initiation of treatment with gabapentin in the population with acute SCI. Gabapentin, although used commonly, is not started in all patients with acute SCI but is often started at the onset of neuropathic pain. If gabapentin is found to be more effective when initiated early, it would be reasonable to start gabapentin immediately following acute SCI in all patients in whom it is not otherwise contraindicated.

1. Objectives

- Primary

- To determine if the time from injury influences the prevalence of neuropathic pain in acute SCI
- To determine if the use of gabapentin in the early acute period influences the prevalence of neuropathic pain in patients with acute SCI
- To compare the efficacy of acute versus subacute initiation of gabapentin in treating neuropathic pain in SCI

- Secondary

- To compare the overall pain scores
- To determine the prevalence of neuropathic pain in those with SCI at admission and discharge to the inpatient rehabilitation hospital
- To compare the use of opiates
- To compare the average daily change in Functional Independence Measure (FIM)
- To compare the change in total motor score on the ASIA impairment scale
- To identify side effects of treatment with gabapentin and their frequency

2. Endpoints

Primary

- Presence of neuropathic pain at time of enrollment and again around time of discharge (Douleur Neuropathique 4, DN4)
- Neuropathic pain level (Neuropathic Pain Scale, NPS) at time of enrollment and again around time of discharge

Secondary

- Average pain level recorded in nursing flowsheet (Numeric Pain Rating Scale, NPRS)
- Weekly total use of opiates (total morphine milligram equivalents, MME)
- Change in FIM during rehabilitation
- Change in total motor score on the ASIA impairment scale during entire rehabilitation course

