- Side effects attributed directly to gabapentin in physician documentation and whether or not gabapentin was stopped due to these side effects

3. Design

- Prospective, observational, cohort, single center study
- The study will enroll subjects with acute spinal cord injury who are admitted to acute inpatient rehabilitation at MetroHealth Rehabilitation Institute (MRI).

- After enrollment, subjects will be followed through the end of their acute rehabilitation stay including any interruption in rehabilitation for which they require ED evaluation and/or acute hospital readmission so long as they return to MRI.
- Around the time of enrollment, subjects will be asked to complete the DN4 questionnaire and the NPS.
- Around the time of discharge, subjects will be asked to complete a second DN4 questionnaire and the NPS.
- The remainder of the data collection will be through review of the patient's electronic medical record (EMR).
- Patients will be divided into those who first received gabapentin during their acute inpatient hospitalization, prior to admission to acute rehabilitation, and those who did not. Additionally, the timing of gabapentin initiation will also be recorded.

4. Subject selection

- Study population

Subjects are patients who suffered acute spinal cord injury for which they are admitted to acute inpatient rehabilitation at MRI.
- Inclusion criteria

Subjects who meet all the following criteria may be given consideration for inclusion in this clinical investigation, provided no exclusion criterion is met

 1. Clinical diagnosis of acute spinal cord injury
 2. Admission to MRI for acute inpatient rehabilitation
- Exclusion criteria

Subjects who meet one or more of the following criteria will be excluded from this clinical study.

 1. Unable to communicate verbally or by writing, unable to follow basic instructions, or unable to answer questions regarding their symptoms

5. Subject Accountability

- Point of enrollment

The point of enrollment is the time at which time a subject signs and dates the valid, IRB approved informed consent form. No study-related procedure or assessments can take place until the informed consent form is signed.
- Withdrawal

All subjects enrolled to the study (including withdrawal or lost to follow-up) shall be accounted for and documented.

Reasons for withdrawal include:

 1. Physician discretion
 2. Subject choice
 3. Lost to follow up
 4. Death

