Subjects may withdraw from the study at any time, with or without reason without prejudice to further treatment.

6. Study methods

- Pre-screening

To determine eligibility for enrollment into the study, the inclusion and exclusion criteria must be assessed.

- Informed consent

After a patient has been identified as a potential candidate, based on meeting all inclusion and no exclusion criteria, written Informed Consent must be obtained by asking patients to read and review the valid IRB-approved Informed Consent. The informed consent process will abide by the MetroHealth Medical Center IRB process.

- Initial Visit

The initial visit will occur at or within 7 days of the time of enrollment and admission to rehabilitation

- o Visit Type: Visit to patient while they are admitted to hospital
 - Admission DN4 and NPS

- Final Visit

The final visit will occur at or within 7 days of the time of discharge from MRI

- o Visit Type: Visit to patient while they are admitted to hospital
 - Discharge DN4 and NPS

- Additional data collection: As outlined in Figure 2

The data collection will be completed via review of the EMR of each subject, and will include the following:

- o Demographics
 - Age
 - Sex
 - Race
 - History of drug use
 - History of smoking
- o Home pain medications prior to SCI injury
- o Date of injury
- o ASIA impairment scores (AIS; 1st documented AIS, rehabilitation admission AIS, and rehabilitation discharge AIS)
- o Operative vs nonoperative management of SCI
- o Length of stay in rehabilitation
- o Rehabilitation admission and discharge FIM scores
- o Rehabilitation admission and discharge total motor scores (TMS) as recorded on AIS
- o Pain scores (NPRS)
 - Average score per week from injury as documented in EMR
- o Opiate use
 - Total weekly MME per week from injury

- Side effects
 - Record side effects attributed to gabapentin by treating physician
 - Record if therapy was stopped and why (ineffective, no longer required, adverse reaction)

7. Statistical Analysis Plan

Subject demographics will be summarized by typical descriptive statistics to compare means or medians and measures of variability

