2. Neuropathic pain levels (Neuropathic Pain Scale, NPS) at time of admission and discharge
3. Pain scores (NPRS)
4. Change in pain scores
5. Opiate use (MME)
6. Change in opiate use
7. Average daily change in FIM (calculated [discharge FIM – admission FIM]/LOS)
8. Change in TMS on the ASIA impairment scale during entire rehabilitation course
9. Adverse events

Adverse events will be noted including documented reports of side effects and whether or not drug was stopped due to adverse effects.

11. Amendments

- If a protocol revision is necessary which affects the rights, safety or welfare of the subjects or scientific integrity of the data, an amendment is required.
- Appropriate approvals (IRB) of the revised protocol must be obtained prior to implementation.

12. Deviations

- No changes or deviations from this protocol, except to protect the life and physical well-being of a subject in an emergency will be made.
-

13. Potential risk and benefits

- All the risks are related to the completion of questionnaires and storage of PHI (see Procedure Consent Form).
- The benefits are all related to the future implications of the study on clinical practice and participation will not impact the subjects directly.

14. Informed consent

- Subject participation in this study is voluntary. Informed consent is required from all subjects\.
- The process of obtaining Informed Consent will follow MetroHealth/IRB process
- Refer to Consent Form

15. Bibliography

1. Guy, S., et al. "Anticonvulsant medication use for the management of pain following spinal cord injury: systematic review and effectiveness analysis." *Spinal Cord*, vol. 52, no. 2, 2014, pp 89-96.
2. Burke, D., et al. "Neuropathic pain prevalence following spinal cord injury: A systematic review and meta-analysis." *European Journal of Pain*, vol. 21, no. 1, 2017, pp 29-44.
3. Siddall P.J. & Middleton J.W. "Spinal cord injury-induced pain: mechanisms and treatments." *Pain Management*, vol. 5, no. 6, 2015, pp 493-507.
4. Kramer J.L., et al. "Neuropathic pain following traumatic spinal cord injury: Models, measurement, and mechanisms." *Journal of Neuroscience Research*, vol. 95, no. 6, 2017, pp 1295-1306.
5. Hagen, E. M. & Rekand, T. "Management of Neuropathic Pain Associated with Spinal Cord Injury." *Pain Therapy*, vol. 4, no. 1, 2015, pp 51-65.

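### The motor endpoint takes its baseline after early gabapentin has begun, so any motor benefit gained in the acute stay is subtracted from the early-versus-late comparison

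*Combined protocol and SAP*

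**What the plan says.** The secondary objective in section 1 sets no time window: "To compare the change in total motor score on the ASIA impairment scale". The endpoint in section 2 does: "Change in total motor score on the ASIA impairment scale during entire rehabilitation course". Section 10 repeats it: "Change in TMS on the ASIA impairment scale during entire rehabilitation course".

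The abstraction list in section 6 has two separate entries. One is "ASIA impairment scores (AIS; 1st documented AIS, rehabilitation admission AIS, and rehabilitation discharge AIS", with three time points. The other is "Rehabilitation admission and discharge total motor scores (TMS) as recorded on AIS", with two. A motor score from the first documented examination is not listed.

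Section 3 divides patients into "those who first received gabapentin during their acute inpatient hospitalization, prior to admission to acute rehabilitation, and those who did not".

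The Introduction gives the grounds for expecting a motor effect: "Gabapentin leads to improvement in total motor scores (6-9" and "Animal models suggest it may be neuroprotective in the acute phase of injury".

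Section 7 gives models for neuropathic pain by DN4 and for change on the Neuropathic Pain Scale. It gives none for TMS.

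**The concern.** A change score removes whatever difference already exists at its baseline. Here the baseline is rehabilitation admission, and the early group is by definition already exposed by then. Motor points that early gabapentin adds in the acute hospital raise the early group's admission score and are not counted as gain. The rationale points to the acute phase, so the endpoint is least sensitive where an effect is expected.

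The comparator can include both patients who never receive gabapentin and patients who start it in rehabilitation. Late starters who benefit would do so inside the counted window, while part of the early group's benefit falls outside it. The risk is that a small, null or negative contrast is taken as evidence about early gabapentin when it partly reflects where the window opens. Section 7 specifies no motor analysis that would correct for this.

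**Working it through.** **No figure to reproduce.** The documents give no sample size, effect size, standard deviation or recovery curve for TMS. Every number below is an assumption, used to show direction and range.

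**Step 1: the order of events (from the text).** Early exposure begins before rehabilitation admission (section 3). The first listed TMS is at rehabilitation admission (section 6). The baseline is therefore post-exposure for the whole early group, without any assumption.

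**Step 2: what is subtracted.** Let B be the TMS benefit of an early start by discharge, f the share of B gained before rehabilitation admission, and L the benefit that the comparator gains from gabapentin started in rehabilitation. With equal natural recovery:

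- injury-to-discharge difference = B − L
- rehabilitation-only difference = (1 − f)B − L
- loss = f × B

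With B = 8 points:

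| f | Rehabilitation-only, L = 0 (full +8) | Rehabilitation-only, L = 4 (full +4) |
|---|---|---|
| 0 | +8 | +4 |
| 0.25 | +6 | +2 |
| 0.5 | +4 | 0 |
| 0.75 | +2 | −2 |
| 1 | 0 | −4 |

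At f = 0 nothing is lost. With an untreated comparator (L = 0) this additive model gives attenuation, at most down to zero. Reversal requires (1 − f)B < L.

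In terms of power, assume 50 per group, SD 15 and a two-sided 5% test. The standard error is 15 × √(2/50) = 3. Power is about Φ(8/3 − 1.96) = 0.76 for the full 8 points and Φ(4/3 − 1.96) = 0.27 for the 4 points left at f = 0.5.

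**Step 3: faster recovery to a common plateau.** Assume 20 recoverable points, admission on day 21, discharge on day 56 and an untreated comparator. The gain from day t1 to day t2 is 20 × (exp(−t1/τ) − exp(−t2/τ)), where τ is the recovery time constant. For example, from day 21 to 56, τ = 45 gives 20 × (0.6271 − 0.2881) = 6.78, and τ = 30 gives 20 × (0.4966 − 0.1546) = 6.84.

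| τ, comparator → early (days) | Gain from injury | Difference | Rehabilitation-only gain | Difference |
|---|---|---|---|---|
| 60 → 45 | 12.14 vs 14.24 | +2.1 | 6.23 vs 6.78 | +0.6 |
| 45 → 30 | 14.24 vs 16.91 | +2.7 | 6.78 vs 6.84 | +0.06 |
| 30 → 20 | 16.91 vs 18.78 | +1.9 | 6.84 vs 5.78 | −1.1 |

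**Step 4: sensitivity to the model.** Step 3 lets the faster rate act from the day of injury. If it acts only from start day s, the share still to recover at a later day t is exp(−s/τ_comparator) × exp(−(t − s)/τ_early).

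| τ, comparator → early (days) | s | Difference from injury | Rehabilitation-only difference |
|---|---|---|---|
| 45 → 30 | 7 | +2.4 | +0.6 |
| 45 → 30 | 14 | +2.2 | +1.2 |
| 30 → 20 | 7 | +1.7 | −0.3 |
| 30 → 20 | 10 | +1.7 | about 0 |
| 30 → 20 | 14 | +1.6 | +0.5 |

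If gabapentin instead raises the plateau from 20 to 24 points at τ = 45, the rehabilitation-only gain is 24 × 0.3390 = 8.14 against 6.78 (+1.4). The difference from injury is 24 × 0.7119 − 20 × 0.7119 = +2.8. The direction is kept, and about half the size is lost.

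Attenuation appears in every scenario in which some benefit precedes admission. Vanishing or reversal appears only in some.

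**The case against.** The strongest reply has four parts.

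**The study is not blind to the acute phase.** Admission and discharge TMS are both collected, so a higher level in early starters would be visible. The AIS is taken at first documentation, admission and discharge, so change in grade across the acute stay can be computed. This stands. A reader might infer that the study cannot show any acute-phase motor benefit, and the documents do not support that. What is missing is a motor-score change from the first examination and a stated analysis. Without a first TMS, a higher admission score cannot be separated, on the motor scale, from a milder injury.

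**Benefit may continue in rehabilitation.** Section 3 speaks of first receipt, and nothing says that gabapentin stops at transfer. Benefit after admission is counted. This stands, and it is why the loss is f × B and not all of B.

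**The first examination may not supply a usable baseline.** Section 6 lists the first AIS but no TMS from it, so it would be wrong to say that the first motor score is already being collected. That examination may be incomplete, later than the first dose, or the same as the rehabilitation admission examination. This stands and limits the fix. It does not make a baseline that follows exposure in the whole early group preferable.

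**It is one secondary endpoint of an observational study.** The window is stated consistently and matches the one for FIM, and no motor test is prespecified. This bears on priority. It does not show the window to be neutral for the comparison. Nor is the window forced by enrolment at rehabilitation, because section 6 already reaches back to the injury for weekly pain scores and opiate use.

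**Conclusion.** The concern holds as a matter of timing. The rehabilitation-only change in TMS uses a post-exposure baseline for every early-group patient, and any motor benefit gained before admission is subtracted from the early-versus-late contrast. The size cannot be derived from the documents. On the assumed inputs above, the loss ranges from none (f = 0) to the whole benefit (f = 1).

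A reader might go further and conclude that a true benefit will vanish or turn into apparent harm. The documents do not support that. Such results need a comparator that benefits during rehabilitation, or faster recovery to a common plateau with an early enough start. Other equally assumed patterns keep the direction and lose only part of the size.

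The point concerns a secondary endpoint and leaves the primary pain endpoints untouched. It merits a change because the protocol's own rationale points to the acute phase and the remedy is chart review.

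**What to change.** In sections 2, 6 and 10, add the TMS and date of the first documented ASIA examination, where available, to the data abstracted. For the early-versus-late comparison, analyse discharge TMS (or change from the first examination) adjusted for the first TMS and its day from injury. Report this alongside the rehabilitation-only change, which stays as it is, and state the model in section 7.

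Report how many first examinations are missing or incomplete, how many coincide with the rehabilitation admission examination, and the spread of their days from injury. Flag for each patient whether the examination preceded the first gabapentin dose. State that confounding by indication remains: treatment is not randomised, and the protocol itself notes that gabapentin is often started when neuropathic pain appears.

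The cost is one score and one date per patient, from an examination whose AIS is already on the abstraction list, plus wording in these sections. No visit or patient burden is added. The price is a baseline of uneven completeness and timing, which is why it should sit beside the rehabilitation-only change and not replace it.

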The relationship between the presence of neuropathic pain and: 1) the time from injury; 2) the timing of gabapentin initiation will be evaluated by building logistic regression models with dichotomous neuropathic pain (measured by DN4) as the dependent variable and time as the independent variable. Potential confounding variables will be added to the model if independently associated with the outcome of interest or based on theoretical grounds.

The efficacy of gabapentin by timing of initiation will be analyzed with a regression model with change in pain on the Neuropathic Pain Scale from admission to discharge with timing of gabapentin initiation as the independent variable. Potential confounding variables will be added to the model if independently associated with the outcome of interest or based on theoretical grounds.

8. Data analysis

- All enrolled subjects will be eligible for evaluation.

9. Data Safety/ Monitoring

The PI and co-investigators will monitor the progress of the research study, including assessments of data quality, participant recruitment, accrual and retention, subject's confidentiality, any adverse event(s), and external factors or relevant information that might have an impact on the safety or ethics of the study.

After recruitment, data analysis will occur and any changes to the risk/benefit ratio to study participation will be identified and reported to the IRB. In addition, the PI and co-investigators will meet on an annual basis and reports of the meeting will be submitted to the IRB.

If an adverse event occurs, it will be reported immediately to the MetroHealth Institutional Review Board (IRB). If an unexpected adverse event occurs, the investigators will assess the risk/benefit ratio of the study and submit any modifications deemed necessary to the IRB for approval. At the time of the IRB renewal, the PI will

submit information about the frequency of the monitoring, the dates that the monthly meeting took place, a summary of the cumulative adverse events, external factors or relevant information that might have an impact on the safety or the ethics of the study, and final conclusions regarding changes to the anticipated risk/benefit ratio to study participation and final recommendation related to the continuation, changing, or termination of the study.

10. Study Assessments

1. Assessment of presence of neuropathic pain (DN4) at time of admission and discharge

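### The only defined groups rest on the setting of the first gabapentin dose, and the analysis plan does not say whether timing means that split or days from injury

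*Combined protocol and SAP*

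**What the plan says.** The third primary objective is "To compare the efficacy of acute versus subacute initiation of gabapentin in treating neuropathic pain in SCI". Neither acute nor subacute is defined in days. The Introduction says that if early use proves more effective, "it would be reasonable to start gabapentin immediately following acute SCI" in patients without a contraindication, so the intended conclusion concerns time since injury.

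Section 3 (Design) gives the only rule for forming groups: patients are "divided into those who first received gabapentin during their acute inpatient hospitalization, prior to admission to acute rehabilitation, and those who did not". It then adds that "the timing of gabapentin initiation will also be recorded", without a unit or a time origin.

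Section 7 (Statistical Analysis Plan) does not mention the setting split. Its logistic models have "dichotomous neuropathic pain (measured by DN4) as the dependent variable and time as the independent variable". Its model for change on the Neuropathic Pain Scale (NPS) is specified "with timing of gabapentin initiation as the independent variable". Covariates are left to a rule: "Potential confounding variables will be added to the model if independently associated with the outcome of interest or based on theoretical grounds". None is named.

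The data list in section 6 includes the date of injury, AIS at three points, operative management and length of the rehabilitation stay. Acute stay is not in the text list. The figure to which section 6 refers is not available here and may list it.

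**The concern.** Place of first dose is a poor stand-in for time from injury. A patient with a long acute stay has more days in which to be labelled early, so the label carries acute stay and whatever lies behind it, such as complications or severity of injury.

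The plan itself gives a reason to expect this to matter. The baseline DN4 and NPS are taken around rehabilitation admission, so a longer acute stay means more days since injury at baseline. The first primary objective asks whether time from injury affects the prevalence of neuropathic pain. The split therefore sorts patients partly on a variable that the study treats as a possible determinant of its own primary endpoint.

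At stake is whether a reported early–late difference reflects when the drug was started or how long the patient was in the acute hospital. Section 7 can be read so as to avoid most of this, but it does not commit to that reading. The secondary comparisons (pain scores, opiates, FIM, motor score) have no model at all, which leaves the setting groups as the only defined contrast.

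**Working it through.** The documents give no sample size, alpha, effect size or standard deviation, so there is no figure of the plan's to reproduce. Every number below rests on assumed inputs and illustrates a mechanism; none is an estimate for this study.

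**1. Misclassification, from the definition alone.** Take a first dose on day 15 after injury. With an acute stay of 20 days the patient is in the early group (15 < 20). With a stay of 10 days the patient is not (15 > 10). Time from injury is the same and the group differs.

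**2. Why longer stays drift into the early group.** Assume that start day is exponential with mean 20 days and independent of acute stay L. Then P(early | L) = 1 − exp(−L/20).
- L = 10: 1 − exp(−0.5) = 0.39
- L = 20: 1 − exp(−1) = 0.63

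**3. Resulting imbalance among gabapentin users.** Assumptions: acute stay log-normal with median 10, 14 or 21 days and log-SD 0.6; mean start day 10, 20 or 40; rehabilitation stay 35 days; start day independent of acute stay. This makes nine scenarios.
- Setting split: the early group's mean log acute stay is higher by 0.66 to 1.02 SD. In the central scenario (median stay 14, mean start day 20) it is 0.75 SD, with median stays of 17.5 and 11.2 days.
- Split at a fixed day (the median acute stay): −0.01 to −0.21 SD; −0.08 in the central scenario.
- The two splits disagree for 11% to 19% of users.

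**4. Spurious difference with no timing effect.** If outcome has correlation ρ with log acute stay, the unadjusted difference in outcome SDs is ρ × imbalance.
- Central scenario, setting split: 0.3 × 0.75 = 0.225; 0.5 × 0.75 = 0.375.
- Central scenario, day split: 0.3 × (−0.08) = −0.024.
- ρ = 0: no spurious difference, but the misclassification in step 1 remains.

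**5. False-positive rates.** Central scenario, two-sided 0.05, least squares, 2,000 simulated studies per cell (simulation error about 0.5 percentage points at a 5% rate, from √(0.05 × 0.95/2000)).

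| N, ρ | Setting split | Day split | Continuous days | Setting split + acute stay |
|---|---|---|---|---|
| 100, 0 | 5.1% | 4.1% | 3.6% | 4.7% |
| 100, 0.2 | 10.2% | 4.6% | 5.1% | 4.6% |
| 100, 0.3 | 17.4% | 5.7% | 6.1% | 4.8% |
| 100, 0.5 | 43.8% | 4.9% | 7.4% | 5.6% |
| 200, 0.3 | 34.0% | 6.6% | 7.8% | 5.8% |

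Continuous days keeps a small excess because, among users, start day is still weakly correlated with acute stay (0.10): a longer total stay leaves more time for a late start. That is a reason to adjust for acute stay as well as to redefine exposure.

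**6. What a days-based exposure does not cure.** Steps 3 to 5 make start day independent of severity. Now assume instead that sicker patients start sooner (start day with mean 14, multiplied by exp(−0.4 × standardised severity)) and that severity explains half the outcome variance. A 12-day split is then spuriously off by roughly 0.3 to 0.4 SD, depending on the remaining inputs, although timing has no effect.

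**The case against.** The strongest reply is that the setting split may never enter the analysis. Section 7 does not mention it, names time and timing of initiation as the independent variables, and echoes the section 3 sentence about recorded timing. A regression on days from injury is a natural reading, and it is close to the change proposed here. This stands in part. A reader might infer that the primary contrast is confounded by construction, or that the plan uses setting instead of days. The documents do not support that. They permit a days-based analysis and fail to commit to one, since no unit, time origin or functional form is given.

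Second, confounders may be added on theoretical grounds, and AIS, motor scores and operative management are collected. Adjusting the setting split for acute stay returned false positives to about 5% to 6% in the simulation. This stands as well, but no covariate is fixed and acute stay is not in the text list, so the protection is optional.

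Third, the size is assumption-driven. The NPS outcome is a change score, in which stable severity partly cancels, so its correlation with acute stay may be low. This stands, and it is why no magnitude is claimed for this study.

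Fourth, days from injury is no cure. The Introduction says gabapentin is often started when neuropathic pain begins, which is confounding by indication. Some starts also precede the baseline NPS, so part of any drug effect is already in the baseline. Both points stand and limit what the fix can deliver.

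**Conclusion.** The point holds as an undefined exposure with a foreseeable bias under one of its two readings. Three facts carry it: the only written groups are by setting, section 7 does not say which exposure its models use, and acute stay is not a prespecified covariate.

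The misclassification of time from injury follows from the definition and needs no assumption. A spurious timing difference needs acute stay to be related to outcome, which the documents neither establish nor quantify. On the assumed inputs, the bias of the unadjusted split runs from nothing at zero correlation to a false-positive rate several times the nominal 5% at moderate correlation.

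A reader might also infer that moving to days from injury brings the bias to zero. That would need start day to be unrelated to the patient's condition, which the Introduction's own account of when gabapentin is started contradicts. The change is worth making before analysis because it ties the exposure to the question and costs little.

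**What to change.** In sections 3 and 7:

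- Define the exposure among gabapentin users as days from injury to first dose, with injury as the stated origin. Use it as a continuous term, or with one cut-off fixed before analysis. The injury date and start timing are already to be collected.
- Analyse patients who never receive gabapentin as a separate group. They have no start day, and the present comparison group mixes them with later starters.
- Prespecify days from injury to rehabilitation admission, and severity as first documented AIS, as covariates. Record the rehabilitation admission date if the data form does not already hold it.
- Apply the same exposure definition to the secondary comparisons, and name their models.
- Keep the setting split as a descriptive or sensitivity comparison only.
- State that these steps reduce the bias but do not remove confounding by indication, or the problem that some starts precede the baseline NPS.

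The cost is mainly wording, plus a little more analysis. Group sizes may be less balanced than under the setting split.
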